5.1.4 Coformulation Phase for MK-1308A (Arms I and K)

The purpose of the coformulation phase is to evaluate safety, PK, and efficacy for MK-1308A, a coformulation of 25 mg MK-1308 and 400 mg pembrolizumab, 17.5-mL fill in a 20-mL vial. The coformulation PK data will be compared to the data generated in the efficacy expansion phase when these drug products were individually co-administered at the same dose level and schedule. Arm I is applicable only to sites in Israel, New Zealand, and Australia. Arm K is applicable only to sites in mainland China.

Arm I (n= up to 20) will enroll participants with advanced/metastatic solid tumors. Participants will receive MK-1308A on a Q6W schedule starting on Cycle 1, Day 1 for up to 18 cycles (~ 24 months).

Arm K (n= up to 20) will enroll participants who reside in China with advanced solid tumors. On Cycle 1, Day 1 and for all subsequent cycles, participants will receive MK-1308A on a Q6W schedule continuously for up to 18 cycles (up to 24 months).

Data from Arm K will be used to demonstrate acceptable safety and PK of MK-1308A in Chinese participants and will inform the use of MK-1308A in China in future studies,

independent of tumor type. Chinese participants who reside in China will only enroll in Arm K.

MK-1308A may be considered as tolerant if one or less participant of the first 3 experience a DLT, or if 2 or less participants of the first 6 experience a DLT (1/3 or $\leq 2/6$) for each sub-cohort (Table 1).

Number of Toxicities		f Participants Treated Current Dose
	n=3	n=6
0	S	S
1	S	S
2	DU	S
3	DU	DU
4		DU
5		DU
6		DU
S=stay at the same dose; DU=De-e Modified mTPI table based on targ		

Table 1Toxicity Assessment

Treatment Allocation

Treatment allocation for dose escalation, dose confirmation, and coformulation Arms I and K will be accomplished by non-random assignment. During the dose confirmation phase when more than 1 treatment arm is open for enrollment of NSCLC participants, IVRS/IWRS will distribute successive participants across all open treatment arms in each phase to minimize selection bias. Each new arm (if applicable) will open for enrollment without delay once the DLT observation period of the previous dose cohort is completed and a dose escalation or cohort expansion decision is made. In the efficacy expansion phase, randomization by IVRS/IWRS will be implemented with equal randomization ratio whenever at least two of the Arms F and G are open for enrollment. (Note: this is a true randomization which is different from the assignment methodology in dose confirmation).

ORR as assessed by the investigator is a secondary objective in the dose escalation phase, dose confirmation phase, and coformulation phase (Arms I and K). The progression-free survival according to RECIST v1.1, as well as overall survival, will be evaluated as exploratory endpoints. In the efficacy expansion and coformulation phases, ORR and PFS will also be assessed by iRECIST.

In participants who have initial evidence of radiological progressive disease by RECIST 1.1, it will be at the discretion of the investigator whether to continue a participant on study treatment until repeat imaging is obtained. This clinical judgment should be based on the participant's overall clinical condition, including performance status, clinical symptoms, and laboratory data. Participants may continue to receive study treatment until the tumor

assessment is repeated 4 to 8 weeks later in order to confirm progressive disease by iRECIST per site assessment.

Adverse events will be evaluated by the investigator, according to criteria outlined in the NCI CTCAE, Version 4.03, to establish the safety and tolerability of MK-1308 when administered as monotherapy, in combination with pembrolizumab, or in coformulation as per the primary objective of this study.

There will be no intra-participant dose escalation for participants enrolled in this study. The Sponsor will evaluate DLTs when at least 10 subjects have completed the DLT period to confirm the safety of Arm I. Enrollment will not be paused while this evaluation is performed. The definition of DLTs and criteria for dose modification of MK-1308 are outlined in Section 7.1.1 and Section 7.2.1.

[figure not shown]
Participants may receive study treatment after initiation of combination treatment with MK-1308 plus pembrolizumab for up to 18 cycles (Q6W) or 35 cycles (Q3W), for a total of 24 months. Participants will be treated until progressive disease, unacceptable toxicity, intercurrent illness that prevents further administration of treatment, investigator's decision to withdraw treatment, participant withdrawal of consent, pregnancy of the participant, noncompliance with trial treatment or procedure requirements, participant completes treatment, or administrative reasons requiring cessation of treatment, at which point they will be discontinued from the study.

Specific procedures to be performed during the trial, as well as their prescribed times and associated visit windows, are outlined in the Trial SoA - Section 2. Details of each procedure are provided in Section 9 – Study Assessments and Procedures.

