3.2.1.2 MK-1308A Background

MK-1308A is a novel coformulation of 25 mg MK-1308 and 400 mg pembrolizumab, 17.5-mL fill in a 20-mL single vial. The rationale to develop this single entity product as a FDC includes the following points:

- 1. There is an advantage to using FDCs when there is an identifiable patient population for whom treatment with a specific combination of agents in a fixed ratio of doses has been shown to be safe and effective, and when all of the agents contribute to the overall therapeutic effect [World Health Organization 2005].
- 2. As other anti-CTLA4 agents have not shown significant efficacy when administered as monotherapy, the Sponsor does not plan to develop MK-1308 as a monotherapy agent.
- 3. Data from the dose confirmation phase of this trial (MK-1308-001) show that only 12 (6.7 %) of the 179 patients enrolled to Arms A, B, C and E discontinued the combination regimen of MK-1308 + pembrolizumab due to toxicity and subsequently started pembrolizumab monotherapy. Moreover, most of these patients had recurrent toxicities of equal or worse grade following resumption of pembrolizumab monotherapy, suggesting holding the combination and restarting only pembrolizumab is not protective.
- 4. Pembrolizumab is available as a marketed product and can be used as on-label or off-label if MK-1308A requires discontinuation due to toxicity.

5. An FDC product is formulated in a single vial, which will result in time-conservation and reduced medication error in comparison to preparation of two independent products.

The objective in the coformulation phases of the study is to evaluate the safety, efficacy, and PK of the coformulated product, and to compare these data to that of the single, co-administered products given at the same dose and schedule.

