The dose decision rules are provided for a target number of participants evaluable for DLT. When the actual sample size differs from the target size, a Go-decision for dose escalation or dose confirmation for MK-1308 in combination with pembrolizumab (Cohort 1, 2, and 3, Arm A, B, C, D, E and F) will require that no more than one-fourth of the participants have a DLT. The doses chosen for evaluation for the MK-1308 and pembrolizumab combination are expected to have a DLT rate $\leq 10\%$. This is based on the known DLT rate of 10.7% in the KN-029 study (pembrolizumab combination with ipilimumab in melanoma) using a dose of ipilimumab of 1 mg/kg.

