7.3 Method of Treatment Assignment

Treatment allocation will occur centrally using an interactive voice response system / integrated web response system (IVRS/IWRS). There are 3 planned treatment cohorts (Cohorts 1, 2, and 3) in dose escalation and 5 planned treatment arms (Arms A, B, C, D, and E) in dose confirmation, 2 planned treatment arms in efficacy expansion (Arms F and G), and 3 planned treatment arms in the coformulation phase (Arms I and K). Participants will be allocated to 1 of 13 planned treatment cohorts/arms.

Treatment allocation will be accomplished by non-random assignment in dose escalation, dose confirmation, and coformulation phase. When more than one treatment arm is open for enrollment of participants with NSCLC during dose confirmation, IVRS/IWRS will

Product: MK-1308 Protocol/Amendment No.: 001-12

distribute successive participants across all open treatment arms within each phase to minimize selection bias. Each new arm will open for enrollment without delay once the DLT observation period of the previous dose cohort is completed and a dose escalation or cohort expansion decision is made. In the efficacy expansion phase, participants will be randomly assigned to either Arm F or Arm G with 1:1 randomization ratio until Arm G reaches the total sample size of 40.

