10.9 Sample Size and Power Calculations

The overall sample size in Cohorts 1 through 3, Arm A, B, C, D and E in this study depends on the observed safety profiles of MK-1308 in combination with pembrolizumab. The maximum sample size is 100 in Arm F and 40 in Arm G. For MK-1308A, the coformulated product, the target sample size is 20 in Arm I, and 20 in Arm K. A target total sample size of 348 participants will be used for study planning purposes.

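### Does the MK-1308A dose-limiting toxicity rule in Section 5.1.4 conflict with the rest of the coformulation phase, and does the arm count in Section 7.3 matter?

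*Combined protocol and SAP*

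**What the plan says.** Section 5.1.4 gives a count rule for MK-1308A. The product may be called tolerable with no more than 1 DLT in the first 3, "or if 2 or less participants of the first 6 experience a DLT". The rule is stated per sub-cohort and points to Table 1, which has columns for 3 and 6 participants only. The readable part of its key is "S=stay at the same dose; DU=De-e"; the rest of the footnote, including the target rate, is cut off.

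Later in the same section: "The Sponsor will evaluate DLTs when at least 10 subjects have completed the DLT period to confirm the safety of Arm I". It continues: "Enrollment will not be paused while this evaluation is performed". No count is attached to that evaluation.

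Section 3.2.1.2 describes one product strength: "MK-1308A is a novel coformulation of 25 mg MK-1308 and 400 mg pembrolizumab". Within the coformulation phase, the DLT endpoint (Sections 1 and 4), the evaluability rule (5.1), the DLT window (7.1.1) and the DLT-evaluable population (10.5.1) all refer to Arm I and not to Arm K.

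Section 5.1 has a fallback for review sizes that differ from target, but it is limited to "Cohort 1, 2, and 3, Arm A, B, C, D, E and F) will require that no more than one-fourth" of participants having a DLT. Arms I and K are not on that list.

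Section 7.3 counts "3 planned treatment arms in the coformulation phase (Arms I and K). Participants will be allocated to 1 of 13 planned treatment cohorts/arms". Section 10.9 says: "A target total sample size of 348 participants will be used for study planning purposes".

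**The concern.** Read together, these passages look like a rule written for a different design. It speaks of sub-cohorts, yet Arm I is a single group. It decides at 3 and 6, yet the only evaluation scheduled for Arm I is at 10 or more. Its alternative to staying appears to be de-escalation, yet the readable text describes no lower MK-1308A level. A third coformulation arm counted in Section 7.3 suggests text left over from a larger design.

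The number of participants with a DLT is a primary endpoint for Arm I, and Section 5.1.4 is the only readable place where a DLT count becomes a statement about MK-1308A tolerability. If the sections truly conflicted, two people could apply different rules to the same data and reach different conclusions about the coformulation. A real third arm would also mean that the planned total is too small.

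**Working it through.** **1. The planned total.** Maxima from Sections 5.1.1 to 5.1.4:

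- Cohorts 1 to 3: 14 + 14 + 6 = 34
- Arms A to E: 30 + 30 + 30 + 30 + 14 = 134
- Arms F and G: 100 + 40 = 140
- Arms I and K: 20 + 20 = 40

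Sum: 34 + 134 + 140 + 40 = 348. The stated figure is reproduced exactly with two coformulation arms. This is a planning sum and not a cap on enrollment: the escalation and confirmation maxima give 34 + 134 = 168, while Section 5.5.3.1 speaks of 215 participants analysed in those phases.

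**2. The group count.** Section 7.3 as written gives 3 + 5 + 2 + 3 = 13. The groups it names give 3 + 5 + 2 + 2 = 12. Sections 5.1.4, 10.1 and 10.9 also have only Arms I and K. The 3 and the 13 are therefore wrong for the current plan. No allocation ratio, sample size or analysis is derived from either number.

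**3. The two DLT reviews side by side.**

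| | Count rule and Table 1 | Later evaluation |
|---|---|---|
| Size | first 3, first 6 | 10 or more completers |
| Group | per sub-cohort, undefined in readable text | Arm I |
| Form | permissive (may be considered) | confirmation of safety, no count |
| Enrollment | no pause stated | explicitly not paused |

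Neither excludes the other. Arm F has a similar pattern in Section 5.1.3: a first look at 6 evaluable participants, up to 14 if needed, and a decision on the totality of safety data.

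**4. What Table 1 would do if applied to Arm I.** Let p be the true DLT rate, X6 the number of DLTs in the first 6, and X3 and Y3 the numbers in the first and second three.

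- Look at 6 only: P(X6 ≥ 3). At p = 0.10 this is 1 − (0.5314 + 0.3543 + 0.0984) = 0.0159.
- Looks at 3 and 6: P(X3 ≥ 2) + P(X3 = 1)·P(Y3 ≥ 2) + P(X3 = 0)·P(Y3 = 3). At p = 0.10 this is 0.0280 + 0.243 × 0.0280 + 0.729 × 0.001 = 0.0355.

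| True rate | Look at 6 only | Looks at 3 and 6 |
|---|---|---|
| 10% | 1.6% | 3.6% |
| 20% | 9.9% | 14.8% |
| 25% | 16.9% | 22.9% |

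Section 5.1 expects a rate of 10% or less for the combination doses. These are the ordinary operating characteristics of a small rule; they do not measure a contradiction.

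**5. Whether Table 1 settles the review at 10.** The target is unreadable, so I assumed a uniform prior, an interval of ±5 points around the target and a 0.95 exclusion cut-off, read escalation entries as stay, and read any de-escalation as the table's DU code. Targets of 20% and 25% both reproduce the split in Table 1 (stay up to 1 of 3 and up to 2 of 6). At 10 participants they give a largest stay count of 3 and 4 respectively. The chance of meeting those counts is 0.987 against 0.998 at a true rate of 10%, and 0.776 against 0.922 at 25%. So the printed columns do not fix a count at 10, but the plan does not say that they should.

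**6. What the analysis uses.** Section 10.6.2 lists and summarizes DLTs by arm, in the population defined in Section 10.5.1. Table 1 does not enter that summary.

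**The case for a change.** The strongest opposing case is that nothing readable links the two reviews. Someone with Table 1 in one hand and 10 completers in the other cannot tell which governs, the one-fourth fallback omits Arm I, the sub-cohort term has no referent, and an instruction to de-escalate has nowhere to go with one fixed strength. The remedy would be a few words and a table, and the miscount in Section 7.3 stands whatever the missing text says.

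The miscount and the undefined term both stand. The rest does not amount to a defect. The Table 1 footnote breaks off in the middle of its key, the figure for Arms I and K is not shown, and Sections 10.7 and 10.8 are not readable. The action, the target and a sub-cohort definition could all be there, and text lost that way cannot be counted as absent from the plan. Extending Table 1 to 10 or more participants would add counts that the readable plan does not contain, and they would depend on assumed settings, as step 5 shows. Replacing the sub-cohort wording with Arm I would decide which participants a safety rule governs; that is a clinical and sponsor decision, not an edit.

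**Conclusion.** No change to the plan follows. The 3 and 13 in Section 7.3 are a clerical slip of one arm; the named groups number 12 and account for all 348 planned participants. The rule at 3 and 6 and the evaluation at 10 or more are compatible as an early permissive check followed by a confirming review that does not hold up enrollment. How they connect is a gap that the study team can fill sensibly under the continuing safety review in Section 9.1.8.2.

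The effect on results is nil on the readable text: DLTs are counted and reported by arm whichever reading is taken, and the Arm F and Arm G efficacy analyses are untouched. If Table 1 is applied to Arm I, the early de-escalation signal has probability 1.6% to 3.6% at a 10% DLT rate, rising to 16.9% to 22.9% at 25%.

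This rests on two assumptions: that the cut-off footnote, the unshown figure and the redacted sections contain nothing that contradicts the readable text, and that the evaluation at 10 is meant as a judgment on all the safety data. Which DLT limit or action is clinically right is not judged here.

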5.1.5 Trial Diagram

DOSE ESCALATION PHASE

[figure not shown]

[figure not shown]
In the dose escalation phase: dosing of pembrolizumab begins at Cycle 2 Day 1 following the monotherapy lead-in dose with MK-1308.

In the dose confirmation phase: dosing of pembrolizumab begins at Cycle 1 Day 1.

* A dose level of MK-1308 between 75 mg and 200 mg may be selected based on the totality of data.

[figure not shown]
[†] An interim efficacy analysis will be performed after the first 8 or 14 participants. If there are 0 responses (CR, PR) in the first 8 evaluable participants, or if there is ≤ 1 response (CR, PR) in the first 14 evaluable participants, enrollment of the arm may be stopped early (if the enrollment is not yet complete). A decision will be made at the Sponsor's discretion whether the remaining sample size originally planned for the arm may be allocated to one or more arms in dose confirmation phase if the enrollments are open.

[figure not shown]

*If participants have PD, they may cross over to Arm F, depending on the rules outlined in Section 5.1.

70

5.2 Number of Participants

This study is expected to enroll approximately 348 participants.

5.3 Beginning and End of Study Definition

The overall study begins when the first participant (or their legally acceptable representative) provides documented informed consent. The overall study ends when the last participant completes the last study-related contact, withdraws consent, or is lost to follow-up (ie, the participant is unable to be contacted by the investigator).

5.3.1 Clinical Criteria for Early Trial Termination

Early trial termination will be the result of the criteria specified below:

- Incidence or severity of adverse drug reactions in this or other trials suggest a potential health hazard to participants
- Plans to modify or discontinue the development of the trial drug
- Poor adherence to protocol and regulatory requirements
- Quality or quantity of data recording is inaccurate or incomplete

Ample notification will be provided in the event of decision to no longer supply MK-1308 or pembrolizumab.

5.4 Scientific Rationale for Study Design

5.4.1 Rationale for Endpoints

5.4.1.1 Efficacy Endpoints

For the efficacy expansion (Arms F and G) phase, ORR assessed by BICR based on RECIST 1.1 is the primary efficacy endpoint. The DOR based on RECIST 1.1 as assessed by BICR is a secondary efficacy endpoint for Arms F and G. The ORR assessed by investigator based on RECIST 1.1 is a secondary efficacy endpoint for the rest of the study. Exploratory endpoints include PFS and OS. In addition, ORR and PFS based on irRECIST (in the dose escalation phase and the dose confirmation phase) and iRECIST (in the efficacy expansion and coformulation phases) are exploratory endpoints.

Tumor responses are evaluated using RECIST 1.1, adjusted to follow a maximum of 10 target lesions and a maximum of 5 target lesions per organ followed by irRECIST or iRECIST. Response confirmation per RECIST 1.1 is required.

The irRECIST accounts for the unique tumor response characteristics seen with immunotherapeutic agents. Immunotherapeutic agents such as MK-1308 and pembrolizumab may produce anti-tumor effects by potentiating endogenous cancer-specific immune responses. The response patterns seen with such an approach may extend beyond the typical time course of responses seen with cytotoxic agents and can manifest a clinical response after an initial increase in tumor burden or even the appearance of new lesions. Standard RECIST may, thus, not provide an accurate response assessment of immunotherapeutic agents. These findings support the need to apply a modification to RECIST that takes into account the unique patterns of atypical response in immunotherapy and enables treatment beyond initial radiographic progression. irRECIST will be used by BICR and investigators to assess tumor response and progression and make treatment decisions in the dose escalation phase and the dose confirmation phase.

iRECIST assessment has been developed and published by the RECIST Working Group, with input from leading experts from industry and academia, along with participation from the US Food and Drug Administration and the European Medicines Agency [Seymour, L., et al 2017]. The unidimensional measurement of target lesions, qualitative assessment of non-target lesions, and response categories are identical to RECIST 1.1, until progression is seen by RECIST 1.1. However, if a participant is clinically stable, additional imaging may be performed to confirm radiographic progression. For the efficacy expansion phase, iRECIST will be used by investigators to assess tumor response and progression and make treatment decisions, as per current health authority guidance.

5.4.1.2 Safety Endpoints

The primary safety objectives of this trial include characterizing the safety and tolerability of MK-1308 when used in combination with and in coformulation with pembrolizumab in participants with advanced solid tumors. The primary safety analyses will be based on participants who experience toxicities as defined by CTCAE, Version 4.03.

The attribution to drug, time-of-onset, duration of the event, its resolution, and any concomitant medications administered will be recorded. Safety data will include, but is not

limited to, AEs, SAEs, fatal AEs, and laboratory changes. Furthermore, specific events will be collected and designated as events of clinical interest (ECIs) as described in Section 9.3.7.

5.4.1.3 Pharmacokinetic Endpoints

A secondary objective of this trial is to characterize the PK profile of MK-1308 and pembrolizumab. The serum concentrations of each antibody will be used to determine PK parameters (eg, C_{max} , AUC) for MK-1308 and pembrolizumab. Furthermore, the results of these analyses will be used in conjunction with pharmacodynamics, safety, and ADA endpoints to help assess dosing strategies for MK-1308.

5.4.1.4 Pharmacodynamic Endpoints

A direct receptor occupancy assay to measure target engagement cannot be used as CTLA4 expression on the cell surface of T-cells is transient and tightly regulated. Therefore, post-treatment changes in absolute leukocyte counts (ALC) and expression of T-cell activation markers (for example Ki67, ICOS, and HLA-DR) will be assessed in peripheral blood based on the proposed effect of CTLA4 blockade in the immune priming phase to increase activation and proliferation of T-cells.

5.4.1.4.1 Anti-Drug Antibody Assessment

Formation of ADAs can potentially confound drug exposures at therapeutic doses, and prime for subsequent infusion-related toxicity. Anti-drug antibody response at the beginning of each cycle will be determined to understand drug metabolism, exposure, and safety. Anti-drug antibody response to MK-1308 and pembrolizumab will be evaluated in validated immunogenicity assays.

